8.8 Action Taken for Adverse Event

Action taken in regards to study medication will be defined as:

- None;
- Infusion interrupted and restarted at a later time;
- Infusion stopped and was not restarted at a later time;
- Infusion cycle delayed

8.9 Outcome of Adverse Event

Outcome will be defined as:

- Resolved (with or without sequelae);
- Ongoing;
- Lost to follow-up.

8.10 Coding of Adverse Events

The Medical Dictionary for Regulatory Activities (MedDRA[®]) will be used to code AEs.

8.11 Serious Adverse Event Reporting

An assessment of the seriousness of each AE will be made by the Investigator. Any AE and laboratory abnormality that meets the above seriousness criteria ([Section 8.2](#)) must be reported immediately to Alnylam, always within 24 hours from the time that site personnel first learn of the event. Every SAE must be documented by the Investigator on

the Serious Adverse Event Report form in addition to the AE form in the CRF. All SAEs must be reported regardless of the relationship to study drug.

The initial report should include at least the following information:

- Patient's study number,
- Description and date of onset of the event,
- Criterion for serious, and
- Preliminary assignment of causality to study drug.

SAE reporting will be via electronic data capture (EDC).

To report the SAE, complete the SAE form electronically in the electronic data capture (EDC) system for the study. When the form is completed, [REDACTED] Safety personnel will be notified electronically and will retrieve the form. If the event meets serious criteria and it is not possible to access the EDC system, send an email to [REDACTED] Safety at [REDACTED] or call the [REDACTED] hotline (phone number will be provided in the Study Manual), and fax the completed back-up paper SAE form to [REDACTED] fax number will be provided in the Study Manual) within 24 hours of awareness. When the EDC system becomes available, the SAE information must be entered into the EDC system within 24 hours of the system becoming available. [REDACTED] Safety personnel will be available for SAE reporting on a 24 hour basis. Incoming reports will be reviewed during normal business hours.

Within 24 hours of receipt of follow-up information, the Investigator must update the SAE form electronically in the EDC system for the study and submit any supporting documentation (e.g., patient discharge summary or autopsy reports) to [REDACTED] Safety personnel via fax or e-mail. If it is not possible to access the EDC system, refer to the procedures outlined above for initial reporting of SAEs.

Appropriate remedial measures should be taken by the Investigator using his/her best medical judgment to treat the SAE. These measures and the patient's response to these measures should be recorded. All SAEs, regardless of relationship to study drug, will be followed by the Investigator until satisfactory resolution or the Investigator deems the SAE to be chronic or stable. Clinical, laboratory, and diagnostic measures should be employed by the Investigator as needed to adequately determine the etiology of the event.

The Investigator will be responsible for reporting all SAEs to the local independent ethics committee (IEC) when required by national regulations.

Alnylam or its representative will be responsible for the reporting of all relevant events to the concerned regulatory authorities according to all applicable regulations.

In Europe, in accordance with the Directive 2001/20/EC, the Competent Authorities and the Ethics Committees in the concerned Member States will be notified of fatal and life-threatening Suspected Unexpected Serious Adverse Reactions (SUSARs) as soon as possible but no later than 7 calendar days after Alnylam or its representative has first knowledge of the minimum criteria for expedited reporting. Non-fatal and non-life-threatening SUSARs should be reported no later than 15 calendar days after Alnylam or its representative has first knowledge of them.

The Investigator may be informed by Alnylam or its representative of SAEs from other Investigators or clinical studies which may have relevance to this clinical trial. These SAEs should also be reported promptly to the IEC or Clinical Events Committee (CEC) that approved the study. All SAE reports should be transmitted to the IEC/CEC with a cover letter or transmittal form, and a copy of that transmittal should be maintained in the Investigator's files and forwarded to Alnylam as part of the Trial Master File on study completion.

8.12 Pregnancy Reporting

A female patient with a positive pregnancy test at Screening/Baseline is ineligible for this trial. If a female patient is determined to be pregnant during the course of the study or during the 75 days after receiving the last dose of study medication, the Investigator should report the pregnancy to the CRO and Alnylam within 24 hours of being notified of the pregnancy. Details of the pregnancy will be recorded on the pregnancy reporting form. The patient should receive any necessary counseling regarding the risks of continuing the pregnancy and the possible effects on the fetus.

The pregnancy should be followed by the Investigator until completion. At the completion of the pregnancy, the Investigator will document the outcome of the pregnancy. If the outcome of the pregnancy meets the criteria for an SAE (i.e., postpartum complication, spontaneous abortion, stillbirth, neonatal death, or congenital anomaly), then the Investigator should follow the procedures for reporting an SAE outlined above.

Pregnancy occurring in the partner of a patient participating in the study should also be reported to the Investigator, who will then report this to the CRO and Alnylam. The partner should be counseled and followed as described above.

9 STATISTICAL METHODS

9.1 Sample Size

Based on the number of patients expected to be enrolled in Study ALN-TTR02-002, up to 28 patients are expected to be enrolled in this extension study. Of these patients, up to 25 are expected to be included in the PK/PD subgroup. Any patient with pre-existing cardiac amyloid involvement will be included in the Cardiac subgroup.

9.2 Statistical Methodology

Statistical analyses will be primarily descriptive in nature. Adverse event summaries will include tabulations of all treatment-emergent AEs (TEAEs), treatment-related AEs, SAEs, discontinuations due to AEs, and AEs of various grading severity. By-patient listings will be provided for deaths, SAEs, and AEs leading to discontinuation of treatment.

Descriptive statistics will be provided for clinical laboratory data, vital signs data, and ECG interval data, presented as both actual values and changes from baseline relative to each on-study evaluation. Laboratory shift tables from baseline to worst values will be presented.

For categorical variables, summary tabulations of the number and percentage of patients within each category (with a category for missing data) will be presented. For continuous variables, the number of patients, mean, median, standard deviation, minimum, and maximum values will be presented.

All data will be provided in by-patient listings.

9.2.1 Populations to be Analyzed

The following patient populations (i.e., analysis sets) may be evaluated and used for presentation of the data:

- Full Analysis Set: All patients who were enrolled will be included in the full analysis set. The full analysis set will be the primary set for the analysis of PD data and clinical activity assessments.
- Safety Analysis Set: All patients in the full analysis set who received study drug. The safety analysis set will be used for the analysis of safety assessments.
- Pharmacokinetic (PK) Analysis Set: All patients in the Safety Analysis Set who have adequate data to determine a full PK profile.

9.2.2 Baseline Evaluations

Demographic and baseline disease characteristic data will be summarized. Data to be tabulated will include sex, age, and race, as well as disease-specific information.

9.2.3 Safety Analyses

A summary of study drug exposure, including the durations of the infusions and doses, and the proportions of patients with modifications in the durations of infusions will be produced.

Adverse events will be summarized by MedDRA system organ class and preferred term. Separate tabulations will be produced for all TEAEs, treatment-related AEs (those

considered by the Investigator as at least possibly drug related), SAEs, and discontinuations due to AEs. By-patient listings will be provided for deaths, SAEs, and AEs leading to discontinuation of treatment.

Descriptive statistics will be provided for clinical laboratory data and vital signs data, presented as both actual values and changes from baseline relative to each on-study evaluation and to the last evaluation on study.

Descriptive statistics will be provided for ECG interval data and presented as both actual values and changes from baseline relative to each on-study evaluation and to the last evaluation on study. Details of any abnormalities will be included in patient listings.

9.2.4 Pharmacodynamics

Summary tables and graphical displays of observed values and changes from baseline in serum TTR will be used to assess the durability of suppression over the course of the study. Similar analyses will be performed for the secondary PD biomarkers (RBP and vitamin A).

9.2.5 Pharmacokinetics

Plasma and urine samples will be evaluated using a validated ATTO-Probe-HPLC method to determine siRNA concentration and by LC/MS/MS method for DLin-MC3-DMA and PEG₂₀₀₀-C-DMG concentrations. The concentration of 4-dimethylbutyric acid (metabolite of DLinMC3DMA) in urine will be evaluated by a validated LC/MS/MS method.

Pharmacokinetic analyses evaluation of siRNA, DLin-MC3-DMA, and PEG₂₀₀₀-C-DMG plasma concentration-time profiles. Pharmacokinetic parameter estimates will be calculated for all subjects in the PK/PD subgroup receiving ALN-TTR02 will include, but may not be limited to: C_{\max} ; t_{\max} ; $t_{1/2\beta}$; $t_{1/2\alpha}$; AUC_p , AUC_{0-t} , $AUC_{0-\text{last}}$ and $AUC_{0-\infty}$; λ_z ; CL , V_{ss} , and V_z . The PK profile of each patient will be characterized by noncompartmental and or compartmental analysis of siRNA, DLin-MC3-DMA and PEG₂₀₀₀-C-DMG plasma concentration using validated computer software (WinNonlin[®] or Phoenix[®], Pharsight Corp., Mountain View, California, USA). Parameters will include, but may not be limited to: C_{\max} , t_{\max} , AUC , CL , V_{ss} , and V_z . The AUC will be calculated using the linear trapezoidal method (linear interpolation). Other parameters may be calculated, if deemed necessary. If possible, the terminal elimination phase of the PK profile will be identified and its slope calculated using log-linear regression. The coefficient of determination of the line fitted to the terminal elimination phase will be calculated. Pharmacokinetic parameters describing the systemic exposure of the test article in the test system will be estimated from observed plasma concentration values for each patient.

Population PK analysis of siRNA and possibly DLin-MC3-DMA will be performed by integrating PK/PD and sparse samples collected during the study. A compartmental model will be developed to model the concentration-time data of plasma siRNA and possibly DLin-MC3-DMA. Pharmacokinetic parameters of siRNA and possibly DLin-MC3-DMA will be derived with the population PK models and summarized with descriptive statistics. Other parameters may be calculated if deemed necessary.

A PK/PD analysis will be performed whenever possible. As part of PK/PD analysis, additional PD baseline analysis on serum TTR, RBP, and vitamin A may be conducted to include the PD data obtained during PD recovery after receiving the last dose. A PD analysis to determine PD parameters will be conducted. The extent of suppression of TTR, RBP, and vitamin A will be evaluated and their correlation between TTR versus RBP and vitamin A will also be performed. The PK/PD analysis will include, but not be limited to, the determination of the relationship between exposure to siRNA, DLin-MC3-DMA and PEG₂₀₀₀-C-DMG to the extent of suppression of TTR, RBP, and vitamin A will be evaluated, including their correlation relationship. The PD and PK/PD parameters will include, but not be limited to, descriptive statistics. Other parameters may be calculated if deemed necessary.

The CL_R of siRNA and 4-dimethylaminobutyric acid (metabolite of DLin-MC3-DMA) after dosing with ALN-TTR02 will be determined for the subjects in the PK/PD subgroups and whenever possible for the other subjects in the study. Other parameters may be calculated if deemed necessary.

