- z On Days 0 and 231, patients in the PK/PD subgroup will have PK samples taken pre-dose (within 1 hour of planned dosing start; -5 minutes), EOI (+5 minutes), and 1, 2, 4, 6, and 24 hours postinfusion. In addition, a plasma PK sample will also be collected 3, 7, and 17 days (± 1 day) after dosing with ALN-TTR02 for the study visits noted. The windows for sampling are ± 5 minutes for the 1, 2, 4, and 6 hour sampling periods; and ± 120 minutes for the 24 hour sampling period.
- aa On Days 0 and 231, patients in the PK/PD subgroup will have a urine sample for PK analysis taken pre-dose (within 1 hour of planned dosing start; -5 minutes), EOI (+5 minutes), and 6 and 24 hours postinfusion. In addition, a urine PK sample will also be collected 3, 7, and 17 days (± 1 day) after dosing with ALN-TTR02 for the study visits noted. The windows for sampling are ± 5 minutes for the 1, 2, 4, and 6 hour sampling periods; and ± 120 minutes for the 24-hour sampling period.
- bb Adverse events are to be documented beginning with the initiation of the first infusion.

Table 1-2: Schedule of Assessments for Year 2 — ALN-TTR02 Administered Once Every 3 Weeks

Procedure	Visit Type	Dosing										Mid-year/ Annual Efficacy Assessment	21- and 56-day Follow-up ^a		Early Termination
		55 & 82	58 & 85	61 & 88	64 & 91	67 & 94	70 & 97	73 & 100	76 & 103	79 & 106	81 & 108		109	114	
	Study Day	D378 & D567	D399 & D588	D420 & D609	D441 & D630	D462 & D651	D483 & D672	D504 & D693	D525 & D714	D546 & D735	D560 & D749	D756	D791	N/A	
	Window	±3D	±5D	±5D	±5D	2D to 7D									
Physical Examination												X	X	X	
Weight ^b	X	X	X	X	X	X	X	X	X	X	X	X	X	X	
Vital Signs ^c	X	X	X	X	X	X	X	X	X	X	X	X	X	X	
12-lead ECG ^d												X	X	X	
Hematology ^e											X		X	X	
Serum Chemistry and Urinalysis ^e					X					X		X	X	X	
Thyroid Function Tests and Coagulation Studies ^e										X		X	X	X	
Ophthalmology Exam											X			X	
PD Assessments:															
TTR protein (ELISA and turbidimetric) ^f	X	X	X	X	X	X	X	X	X	X	X	X	X	X	
RBP and Vitamin A ^f					X					X	X	X	X	X	
Other Assessments:															
Exploratory Biomarkers ^g					X					X					
Anti-drug Antibodies										X ^h					
Pharmacoeconomics Questionnaire											X			X ⁱ	

Procedure	Visit Type											Mid-year/ Annual Efficacy Assess- ment	21- and 56-day Follow-up ^a		Early Termination
		55 & 82	58 & 85	61 & 88	64 & 91	67 & 94	70 & 97	73 & 100	76 & 103	79 & 106	81 & 108				

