7.5.1 Plasma Pharmacokinetics

The PK evaluation will include plasma-concentration time profiles for siRNA and the novel lipid components DLin-MC3-DMA and polyethylene glycol (PEG)₂₀₀₀-C-DMG. Details of the PK evaluation and analysis will be described in the PK and PK/PD analysis plan.

Plasma and urine samples will be evaluated using a validated ATTO-Probe-HPLC assay to determine siRNA concentration and by LC/MS/MS for DLin-MC3-DMA and PEG₂₀₀₀-C-DMG concentrations.

Blood sample collection times are included in the schedule of events (see Table 1-1 and Table 1-2 or Table 12-1 and Table 12-2). For all patients, plasma PK samples will be collected pre-dose (within 1 hour of planned dosing start) EOI and 1 hour post-dose at first dose and every dose up through, and including, the 3 month dosing visit, and then at 6, 9, and 12 month dosing days. Plasma PK samples will be collected pre-dose (within 1 hour of planned dosing start) and EOI at 15, 18, 21, and 24 month visits. The EOI will usually occur at 70 minutes after the start of the infusion, except in patients where the infusion has been prolonged. In addition, if the infusion is stopped and the site is considering restarting the infusion, a PK blood sample will be taken while the infusion is stopped. All PK samples will be collected according to the schedule of assessments when the dose is completed (i.e., all post-infusion times are relative to the EOI, regardless of the duration of the infusion). Plasma PK samples will also be collected at the Mid-year and Annual visits (1 sample collected on each of the 2 study visit days), the 21- and 56-day Follow-up visits, and the Early Termination visit.

For the PK/PD subgroup subjects, samples will be collected pre-dose, and at 1, 2, 4, 6, and 24 hours post-infusion; and at 3, 7 and 17 days post-dose for the first dose and the 8 and 24 month dosing days.

Pharmacokinetic analyses will consist of either a noncompartmental and/or compartmental analysis of plasma siRNA, DLin-MC3-DMA (lipid), and PEG₂₀₀₀-C-

DMG (lipid). Details of the PK evaluation and analysis will be described in the PK and PK/PD analysis plan. Pharmacokinetic parameter estimates to be calculated may include, but may not be limited to:

- Observed C_{max} .
- Time of observed maximum concentration (t_{max}).
- Partial area under the plasma concentration-time curve (AUC_p).
- Area under the plasma concentration-time curve to the last measurable concentration (AUC_{0-t}).

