4.5.1. Study Variables

4.5.1.1. Concentration Data

Urinary concentrations of ALN-18328 (siRNA) and 4-dimethylaminobutyric acid, as well as plasma concentrations of ALN-18328, DLin-MC3-DMA and PEG₂₀₀₀-C-DMG will be obtained. Concentration values that are below the limit of quantification (LLOQ or BLQ) will be set to zero for analysis.

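### Linear trapezoidal AUC over post-infusion gaps of 18 h to 10 days overstates each exponentially declining segment; linear-up/log-down would be a cheap improvement

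*Protocol*

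**What the plan says.** Protocol 9.2.5 sets one integration rule for noncompartmental AUC: "The AUC will be calculated using the linear trapezoidal method (linear interpolation"). The same section adds: "If possible, the terminal elimination phase of the PK profile will be identified and its slope calculated using log-linear regression". It lists alpha and beta half-lives among the parameters.

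The rich profiles are taken in the PK/PD subgroup at the first dose and at the 8- and 24-month doses. Protocol 7.5.1 says "samples will be collected pre-dose, and at 1, 2, 4, 6, and 24 hours post-infusion; and at 3, 7 and 17 days post-dose". Footnote z of Protocol Table 1-1 adds an end-of-infusion (EOI) sample and repeats that "a plasma PK sample will also be collected 3, 7, and 17 days", with a window of one day either way. On infusion length: "The EOI will usually occur at 70 minutes after the start of the infusion".

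The rule is not the only route to the parameters. Protocol 9.2.5 says "The PK profile of each patient will be characterized by noncompartmental and or compartmental analysis", and Protocol 7.5.1 says "Details of the PK evaluation and analysis will be described in the PK and PK/PD analysis plan". That plan is not among the documents.

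SAP 4.5.1.2 lists AUC over a dosing interval, AUC(τ), together with CL, Vss and Vz, and gives no integration rule. SAP 4.5.2 summarises AUC(τ) for Day 1 only, and CL, Vss and Vz at one later visit. SAP 4.5.1.1 says: "Concentration values that are below the limit of quantification (LLOQ or BLQ) will be set to zero for analysis".

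**The concern.** The protocol treats the decline as exponential when it estimates the terminal slope and as a series of straight lines when it computes AUC. The two differ little when samples are close together. Here they are not: after the 6-hour sample the gaps are 18 hours (6 to 24 h), 2 days (24 h to day 3), 4 days (days 3 to 7) and 10 days (days 7 to 17). With the one-day windows, the last gap can be 8 to 12 days.

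The error is systematic, so more patients would not average it out. It would pass to any clearance computed as dose divided by AUC, and to Vz, which is that clearance divided by the terminal slope. Vss also depends on the first-moment curve, so the direction of its error is not established here.

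The SAP's rule for values below quantification (BLQ) could add to this. If a late BLQ value enters AUC(τ) as zero, a straight line runs from the last measurable value down to zero, possibly over 10 days.

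**Working it through.** The documents state no AUC, clearance or half-life, so there is no figure of the plan's to reproduce. Sampling times and infusion length come from the protocol; all half-lives below are assumptions.

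**1. One declining segment.** For an exponential fall over a gap g with half-life h, let x = ln 2 × g/h. Then linear area / true area = (x/2) × (1 + e^−x)/(1 − e^−x).

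| Half-lives in the gap | 1 | 2 | 3 | 4 |
|---|---|---|---|---|
| Linear / true | 1.040 | 1.155 | 1.337 | 1.571 |

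For the 10-day gap this gives 3.47 at a half-life of 1 day, 1.84 at 2 days, 1.41 at 3 days, 1.16 at 5 days and 1.04 at 10 days.

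**2. Whole profile, one half-life.** Take a constant 70-minute infusion (T = 70/60 h) with k = ln 2/h. The concentration is proportional to 1 − e^−kt up to T and falls as e^−k(t−T) afterwards. Sample at pre-dose, EOI, 1, 2, 4, 6 and 24 h, days 3, 7 and 17, and the next pre-dose at day 21. Compare the linear trapezoid with the exact area to day 21. The clearance ratio is the reciprocal.

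| Half-life | AUC, linear / true | CL, linear / true |
|---|---|---|
| 0.25 h | 0.95 | 1.05 |
| 0.5 h | 0.99 | 1.01 |
| 1 h | 1.07 | 0.94 |
| 2 h | 1.22 | 0.82 |
| 4 h | 1.26 | 0.79 |
| 24 h | 1.15 | 0.87 |
| 2 days | 1.13 | 0.89 |
| 3 days | 1.10 | 0.91 |
| 5 days | 1.06 | 0.95 |
| 10 days | 1.02 | 0.98 |
| 20 days | 1.005 | 0.995 |

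The shortest half-lives reverse the sign because the concentration curve during the infusion is concave, and the single straight line from pre-dose to EOI lies below it.

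**3. Which gap matters.** At a half-life of 4 h, the 6-to-24 h gap contributes about 22 percentage points of the 26. At 2 to 3 days, the 10-day gap contributes about 7 points. The longest gap is therefore not always the main source.

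**4. Whole profile, two phases.** Use 48 profiles: alpha half-life 0.5, 1, 2 or 3 h; beta half-life 1, 2, 3 or 5 days; beta share of the initial concentration 1%, 5% or 10%. The area runs to day 17.

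| Rule | Range of AUC error | Median | Mean absolute error |
|---|---|---|---|
| All linear | +3.6% to +25.6% | +12% | 13% |
| Linear-up/log-down | −6.0% to +6.9% | +1.6% | 3% |

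Linear-up/log-down was closer to the truth in 47 of the 48. Clearance under the linear rule: 1/1.036 = 0.965 and 1/1.256 = 0.796, so about 3% to 20% too low. A tail extrapolated to infinity does not use the trapezoid and dilutes the error where that tail is large.

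**5. BLQ set to zero.** Suppose day 7 is the last measurable value, C7, and day 17 is BLQ. Integrating the zero gives ½ × 10 × C7 = 5.0 C7 days. The exponential area over the same 10 days is C7 × (h/ln 2) × (1 − 2^(−10/h)): 1.44 C7 days at a half-life of 1 day and 2.80 C7 days at 2 days.

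**The case against.** The linear trapezoid is a recognised, pre-specified rule, applied alike to every patient and visit. Linear-up/log-down is not exact either. It keeps the linear infusion rise and misfits a segment in which two phases mix. At a single half-life of 0.5 h or less it does worse than the linear rule: about 0.90 of true at 0.5 h, against 0.99. This stands. The recommendation is a better convention over the plausible middle range, not the repair of a mistake.

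The size of the bias belongs to the assumed half-lives. This also stands; the documents give none.

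A reader might infer that every reported AUC and clearance is biased in one direction. The documents do not support that. The direction is certain for each exponentially declining segment but not for the whole profile. Compartmental and population-PK clearance do not use the trapezoid, and details are deferred to a plan that is not available here.

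A reader might also infer that exposure-response results, or comparisons between the siRNA and the two lipids, are compromised. SAP 4.5.2 names Cmax as the exposure measure, and Cmax does not depend on the integration rule. Protocol 7.5.1 does name AUC as an example exposure measure, but a roughly common proportional error within one analyte leaves r² and the p-value for the slope unchanged. No comparison of exposure between analytes is planned.

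On BLQ, the protocol's AUC to the last measurable concentration excludes later zeros by definition, so only AUC(τ) could be affected. Neither document says the zeros are integrated.

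What survives is that the protocol's only stated AUC rule is linear on every segment, the SAP does not change it, and neither document says which analysis yields the reported clearance and volumes.

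**Conclusion.** The point holds as a cheap improvement to a descriptive analysis. At the planned sampling times the all-linear rule overstates each exponentially declining segment. Over the assumed two-phase range, whole AUC is about 4% to 26% too high and a clearance derived from it about 3% to 20% too low. With a single half-life, the bias is slightly reversed at about 0.5 h or less and is 2% or less at about 10 days or more.

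The effect reaches AUC, noncompartmental CL and volume summaries, and the protocol's AUC-based PK/PD exploration. PK is a tertiary objective with no hypothesis test. The primary safety objective, the secondary TTR and mNIS+7 results and the SAP's Cmax-based analysis are unaffected.

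**What to change.** In Protocol 9.2.5 and SAP 4.5.1.2:

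- Use the linear trapezoid while concentrations rise and the logarithmic trapezoid while they fall, with actual sampling times measured from the end of infusion. If the linear rule is kept, give the reason.
- For AUC(τ), treat BLQ values after the last measurable concentration as missing rather than zero, and say whether the remainder to day 21 is extrapolated with the terminal slope.
- State whether reported CL, Vss and Vz come from noncompartmental or compartmental analysis.

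This is one software option and a few sentences, with no new samples or data. The downside is comparability: AUCs from earlier studies that used the linear rule would need re-running. If the observed early half-life proves to be about 0.5 h or less, log-down loses its advantage, so reporting both rules once as a sensitivity check would be sensible.
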